### 4.3.3 Co-enrolment

Co-enrolment will be permitted with observational studies (including those collecting samples) without prior agreement needed.

The Trial Management Group will consider co-enrolment with other interventional studies where there is no possible conflict with the MOSAICC Trial objectives. We will follow previous experience and existing guidelines from the UK Critical Care Research Group regarding co-enrolment to other clinical trials to maximise patient involvement in research. Co-enrolment agreements will be put in place on a case-by-case basis.

### 4.3.4 Screening

Potentially eligible patients admitted or accepted for admission to the participating ICU will be screened against the inclusion/exclusion criteria by the local clinical team, supported by the site research team. Eligibility can be confirmed by a medical practitioner or a nurse, where delegated by the PI.

Screening Logs will record enrolled patients, reasons for exclusion and the reason eligible patients are not enrolled.

## 4.4 Recruitment and consent

### 4.4.1 Randomisation

Participants will be randomised 1:1 to receive IV 8.4% w/v sodium bicarbonate infusion (intervention) or no IV sodium bicarbonate (comparator) with randomised permuted blocks of variable block sizes, stratified by site.

A central web-based randomisation/treatment allocation system will be used. The service will be available 24 hours a day, seven days a week. The research/clinical team will randomise and co-

ordinate the treatments. Sodium bicarbonate will be available on the critical care unit and, following prescription, will be administered by one of the clinical team caring for the patient.

Following randomisation into MOSAICC, each participant will be assigned a unique MOSAICC Trial Number and a CRF will be completed by the local team (see section 4.7.4)

#### 4.4.1.1 Blinding

MOSAICC is an open trial. With frequent blood gas measurements required as part of routine critical care practice, it is impossible to blind the effects of intravenous administration of sodium bicarbonate.

#### 4.4.2 Consent procedures

Patients eligible for MOSAICC become so during a period of critical illness when they may be lacking mental capacity and/or the ability to communicate effectively. Moreover, the emergency clinical situation can cause profound distress for relatives, raising ethical concerns both about the burden of trying to understand the trial and the ability of a Personal Legal Representative (i.e. relative or close friend) to provide an opinion about trial participation during a time of great distress. For these reasons, attempts to obtain either prior informed consent from the patient, or the prior opinion of a Personal Legal Representative, are inappropriate.

MOSAICC will adopt a research without prior consent model (also referred to as 'deferred consent'), whereby eligible patients will be randomised prior to deferred consent to continue from a Personal (family member/close friend) or Professional (independent clinician) Legal Representative and/or deferred consent from the patient themselves. This is an accepted consent model in adult emergency and critical care research where participants are likely to lack capacity and minimises the distress and burden on families. This consent model will be covered by an Emergency Waiver of Consent under the Medicines for Human Use (Clinical Trials) Regulations 2004 (approved by the North West – Greater Manchester Central Research Ethics Committee (reference: 21/NW/0228)).

The PI retains overall responsibility for the informed consent of participants at their site and must ensure that any person delegated responsibility to participate in the informed consent process is duly authorised, trained and competent to participate according to the ethically approved protocol, principles of Good Clinical Practice (GCP) and Declaration of Helsinki. If delegation of consent is acceptable then details of above should be provided for the delegated individual.

In the rare situation where a patient has been deemed by the treating clinical team to have full capacity and is able to give informed consent at the point of meeting the eligibility criteria, they will be approached directly prior to randomisation for full written informed consent, or verbal or other non-written (e.g. through blinking or hand movement) consent to take part in MOSAICC. If they provide verbal or other non-written consent, they will then be followed up for full written informed consent, in line with the procedures outlined in section 4.4.2.1. If such a participant who gave prospective verbal/non-written consent subsequently lost mental capacity, the opinion of a Personal or Professional Legal Representative should be sought to advise on their continuation in the trial (see sections 4.4.2.2 and 4.4.2.3).

##### 4.4.2.1 Patient informed deferred consent

Following randomisation, patients will be approached by a delegated member of the site research team once deemed to have full capacity to provide informed deferred consent. It is anticipated that this first approach will occur within 24-48 hours of regaining capacity, however this will depend on the patient's condition and will be left to the discretion of the clinical team. A Participant Information Sheet (PIS) will be given to the patient. The PIS will provide information about the background/rationale for the trial, what participation means for the patient (e.g. data collection,

follow-up questionnaires), confidentiality and data protection and the future availability of the trial results. Patients will be given time to read the PIS and have an opportunity to ask any questions they may have about participation in MOSAICC.

A Consent Form will be provided indicating that: the information given, orally and in writing, has been read and understood; participation is voluntary and can be withdrawn at any time without consequence. The Consent Form will also cover consent for access to medical records for on-going data collection and follow-up.

After verifying that the PIS and Consent Form are understood, the person seeking consent will invite the patient to sign the Consent Form and will then add their own name and countersign it. A copy will be given to the patient, a copy placed in the patient's medical notes and the original kept in the Investigator Site File. If the patient is unable to physically sign the Consent Form (e.g. due to weakness, reduced dexterity), an independent witness (i.e. someone not involved in the trial) can sign on their behalf.

In the situation where a patient is approached in hospital but wishes to have more time to consider participation, they can request to be approached via the method detailed in section 4.4.2.4.

#### 4.4.2.2 Personal Legal Representative consent

It will sometimes not be possible to involve trial participants in the consenting process early on. Instead, consent will be obtained from patients once they have stabilised and are deemed to have capacity.

In the interim, once notified of the enrolment of a patient into MOSAICC, a delegated member of the site research team will approach the Personal Legal Representative (in person or via telephone) as soon as appropriate and practically possible to discuss the trial and seek their opinion as to the patients' likely wishes and feelings regarding participating in the trial. Ideally, this approach would take place within 24-48 hours of randomisation, but once the patient's medical situation is no longer an emergency. The Personal Legal Representative will be a person not connected with the conduct of the trial who is: suitable to act as the legal representative by virtue of their relationship with the adult, and available and willing to do so.

Where approached in person, the Personal Legal Representative will be provided with a Personal Legal Representative Information Sheet, containing all of the information provided on the PIS, supplemented with information on why the Personal Legal Representative has been approached at this stage. Personal Legal Representatives will be given time to read the Personal Legal Representative Information Sheet and have an opportunity to ask any questions they may have about the patients' participation in the MOSAICC.

A Personal Legal Representative Consent Form will be provided indicating that: the information given, orally and in writing, has been read and understood; the patients' participation is voluntary and can be withdrawn at any time without consequence; and that, in the Personal Legal Representative's opinion, the patient would not object to taking part in the trial.

After verifying that the Personal Legal Representative Information Sheet and Consent Form are understood, the person seeking opinion will invite the Personal Legal Representative to sign the Consent Form and will then add their own name and countersign it. A copy will be given to the Personal Legal Representative, a copy placed in the patient's medical notes and the original kept in the Investigator Site File.

If a Personal Legal Representative advises that, in their opinion, the patient would not choose to participate in the trial, then the trial treatment will be stopped (if ongoing) and the Personal Legal Representative asked whether, in their opinion, the patient would be willing to continue with ongoing data collection.

Where a Personal Legal Representative is unable to visit the patient in hospital (e.g. due to infection control measures), this consultation may take place over the telephone. The consultation

should be conducted by an experienced member of the site research team with knowledge of intensive care. The telephone consultation should be witnessed by another member of staff. The Personal Legal Representative Information Sheet may be sent to the Personal Legal Representative by email or by post. The outcome of the consultation will be documented and signed by person seeking opinion on the Personal Legal Representative Telephone Consent Form, countersigned by the witness.

Upon patient recovery, the patient will be approached directly for informed deferred consent (see section 4.4.2.1). The patient's decision will be final, and will supersede the Personal Legal Representative, where there is disagreement.

#### 4.4.2.3 Professional Legal Representative consent

In the situation where the patient has died, a Professional Legal Representative will be appointed. The Professional Legal Representative may be an independent doctor (i.e. not involved in the trial) or a person nominated by the NHS Hospital Trust. Consent on behalf of the patient from the Professional Legal Representative will be sought in the same manner as for the Personal Legal Representative.

A Professional Legal Representative will also be approached in the rare situations where no Personal Legal Representative is available (or one is available, but does not wish to be consulted). Upon patient recovery, the patient will be approached directly for informed deferred consent (see section 4.4.2.1). The patient's decision will be final, and will supersede the Professional Legal Representative, where there is disagreement.

#### 4.4.2.4 Discharge prior to consent being confirmed

In the situation where the patient is discharged from hospital prior to confirming their consent decision, an experienced member of the site research team with knowledge of intensive care will attempt a phone call to the patient within 14 working days of ultimate hospital discharge to: inform them of their involvement in MOSAICC; provide information about the trial; and seek their consent. The telephone consultation should be witnessed by another member of staff. The Patient Information Sheet may be sent to the patient by email or by post. The outcome of the telephone call will be documented and signed by the person seeking consent on the Telephone Consent Form, countersigned by the witness.

If there is no response to at least three telephone call attempts, or, where no telephone number for the patient is documented, then the patient will be approached by post. The patient will be sent a covering letter, personalised by the most appropriate clinical/research team member, and a copy of the PIS and Postal Consent Form. The letter will direct the patient to the PIS for detailed information on the trial and provide contact details for if the patient wishes to discuss the trial further. In addition, the letter will confirm that if no Consent Form is received within four weeks of the letter being sent, then the participant's data will be included in the trial unless they notify the site research team otherwise.

Both methods described above will provide patients with the opportunity to opt out of on-going data collection or follow-up questionnaires. A decision to opt out during the telephone call will be documented by the person seeking consent on the Telephone Consent Form. For the postal approach, the patient can actively opt out by returning the Postal Consent Form or using the telephone contact details provided on the PIS, at any point during the trial.

If the participant is transferred to another hospital participating in MOSAICC before the consent procedures are complete, then the local research team will contact the research team at the receiving hospital to handover the consenting procedures.

## 4.5 Trial interventions

### 4.5.1 Intervention – Sodium Bicarbonate 8.4% w/v for intravenous administration

Participants randomised to the intervention group will receive sodium bicarbonate 8.4% w/v for intravenous (IV) administration aiming to restore pH to  $\geq 7.30$ .

#### 4.5.1.1 Regulatory status

In the UK, IV sodium bicarbonate 8.4% w/v has marketing authorisation (MA) held by Macarthys Laboratories Ltd. and will be used in its marketed presentation and packaging bearing the MA number: PL 01883/0023.

#### 4.5.1.2 Dosage schedule

50 ml of IV 8.4% w/v sodium bicarbonate administered over 30-60 minutes. Arterial blood gas (ABG) analysis should be performed 1-2 hours after each infusion.

Participants should be assessed for response to treatment and repeated doses should be administered depending on subsequent pH readings and clinical status (including haemodynamic monitoring heart rate, blood pressure), as well as blood gas analysis (including  $p\text{CO}_2$ ,  $\text{HCO}_3^-$  and electrolytes) up to a maximum of 500 ml per 24-hour period (see *MOSAICC Intervention flow diagram*).

#### 4.5.1.3 Intervention period

The intervention period will continue until discharge from critical care, initiation of KRT or 90 days, whichever comes first. As such, participants will be continually monitored (as per MOSAICC Intervention flow diagram) and if a participant's pH drops  $< 7.3$ , at any point during this period, then sodium bicarbonate treatment will continue according to the dosage schedule.

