## 1.2 Sodium bicarbonate

A recent randomised controlled trial (RCT) evaluating the use of sodium bicarbonate in critically ill patients with acidosis found a significant reduction in 28-day mortality (46% sodium bicarbonate vs. 63% control) and use of KRT in a pre-specified subgroup of patients with AKI (n=182). However, such sub-group analyses must be treated with caution, and the authors rightly called for a larger RCT to address this question.

While there are evidence-based recommendations for the use of sodium bicarbonate in other populations, such as for patients with chronic kidney disease (CKD) and end stage renal disease, possible side effects, such as rebound alkalosis, cardiac suppression, potential intracellular acidification due to the accumulation of carbon dioxide and risk of hypocalcaemia, have been identified.

Currently, there is uncertainty among critical care clinicians as to whether sodium bicarbonate should be used for routine treatment of acidosis in patients with AKI. A survey of UK critical care units indicated substantial variation in practice, with 23% of clinicians reporting some use of sodium bicarbonate for patients with moderate acidosis (pH 7.20–7.30), 34% for severe acidosis (pH 7.10–7.20), 21% for very severe acidosis (pH < 7.10) and 22% reporting no use at all. These results are consistent with a similar survey conducted in the US. There is currently little high-quality evidence for the use of sodium bicarbonate in patients with acidosis and AKI which is likely to lead to varied use in critical care units worldwide.

The Multicentre evaluation Of Sodium bicarbonate in Acute kidney Injury in Critical Care (MOSAICC) RCT will address the clinically important question of whether in critically ill adults with metabolic acidosis and AKI, is treatment with IV 8.4% weight by volume (w/v) sodium bicarbonate superior to no IV sodium bicarbonate in terms of all-cause mortality at 90 days (clinical effectiveness) and incremental costs, quality-adjusted life years (QALYs) and net monetary benefit at 90 days (cost-effectiveness). This evaluation will have a large and immediate impact on clinical practice and on patient outcomes in the NHS and worldwide.

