### 4.3.2 Exclusion criteria

1. Respiratory acidosis (acute or chronic)
2. Clinical decision already in place to start patient on kidney replacement therapy (KRT)
3. Deemed unsuitable for KRT
4. Acute diarrhoea, including high output stoma/ileostomy
5. Percutaneous biliary drainage
6. Documented Stage 4 chronic kidney disease (CKD) [eGFR <30ml/min/1.73m^2] or end stage kidney disease (ESKD) on dialysis
7. Known renal tubular acidosis
8. Diabetic ketoacidosis
9. High anion gap acid poisoning (e.g. polyethylene glycol (PEG), aspirin, methanol)
10. Known to be pregnant
11. Symptomatic hypocalcaemia (Ionised calcium <1.05 mmol/L) †
12. Hyponatraemia (Plasma sodium >150 mmol/L) †
13. Severe hypokalaemia (Potassium <3.0 mmol/L) †
14. Solid organ transplant
15. Death perceived as imminent
16. Known hypersensitivity to sodium bicarbonate or to any of the excipients (see section 6.1 of the SmPC)

† Exclusion criteria 11-13 are dynamic, and if corrected, patient may be reconsidered for the trial.

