#### 4.5.4 Monitoring adherence to interventions

In the intervention group, adherence to the protocol will be defined as receipt of IV sodium bicarbonate when pH <7.30 until critical care unit discharge or commencement of KRT. Protocol adherence in the control group will be defined by the absence of IV sodium bicarbonate.

During site set-up and recruitment, sites will receive standardised training materials, including an enhanced site training and education website that explicitly cover the current evidence base, the rationale for the study, and treatment protocols in both groups.

During the study, sites will be provided with individual site reports displaying their adherence data and highlighting areas for improvement. Protocol adherence will also be monitored as part of the central monitoring plan. Non-adherence will trigger a query to the participating site who will be required to provide justification.

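### Section 4.5.4 scores intervention-arm adherence on pH <7.30 alone, so a dose withheld in line with the dosage schedule in section 4.5.1.2 is counted as non-adherence and queried

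*Protocol*

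**What the plan says.** Dosing is set out in Protocol section 4.5.1.2. A 50 ml infusion over 30 to 60 minutes is followed by an arterial gas 1 to 2 hours later. After that, "repeated doses should be administered depending on subsequent pH readings and clinical status", and the same sentence adds the gas results ("as well as blood gas analysis (including" pCO2, HCO3 and electrolytes). The total is capped at 500 ml per 24 hours. The dose row of the Summary gives the same conditions. Section 4.5.1 states the aim as "aiming to restore pH to" 7.30 or above.

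Section 4.5.1.3 sets the period: "The intervention period will continue until discharge from critical care, initiation of KRT or 90 days, whichever comes first". If pH drops below 7.3 "at any point during this period, then sodium bicarbonate treatment will continue according to the dosage schedule". The Summary repeats this.

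Section 4.5.4 then gives the measure for the intervention group: "adherence to the protocol will be defined as receipt of IV sodium bicarbonate when pH <7.30", running until the participant leaves the unit or starts KRT. It does not mention clinical status, pCO2, HCO3, electrolytes or the 24-hour maximum. The same section says that adherence data are fed back in site reports, that adherence is monitored centrally, and that each instance of non-adherence raises a query the site must justify. Adherence also informs the choice of site visits (section 6.2) and is reviewed by the DMEC (section 8.4).

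**The concern.** An adherence measure should tell the oversight bodies whether the protocol was followed. Here the instruction has several conditions and the measure has one. A clinician who reads the gas, applies section 4.5.1.2 and holds a dose has followed the protocol but is recorded as departing from it.

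Two things follow. First, the adherence reported to sites and to the DMEC is too low, because legitimate withholding is mixed with real omissions. Second, the query process pushes sites towards giving a dose that the schedule might have them hold.

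The protocol itself makes such episodes foreseeable. Section 4.3.2 excludes "Respiratory acidosis (acute or chronic" at entry, but participants may stay on the unit for weeks and their acid-base state can change. Section 1.3 reports that IV bicarbonate raised PaCO2 in earlier studies, and section 1.2 lists "potential intracellular acidification due to the accumulation of carbon dioxide" among possible side effects. Section 4.5.3 describes a participant who has had the full daily maximum and still has pH <7.25.

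**Working it through.** The protocol gives no adherence figure to reproduce, so the check sets the sections side by side and asks how each treats the same reading.

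| Situation at a reading of pH <7.30 | Section 4.5.1.2 (reached through 4.5.1.3 and the Summary) | Section 4.5.4 |
|---|---|---|
| Dose held because pCO2 is raised | pCO2 is a named factor, so holding is open to the clinician | Non-adherent |
| Dose held on clinical status (heart rate, blood pressure) | A named factor, so holding is open to the clinician | Non-adherent |
| 500 ml already given in the 24 hours | A further dose would exceed the maximum | Non-adherent if not dosed |

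The first two rows involve judgement, because section 4.5.1.2 names the factors without thresholds. The third does not: dosing breaches 4.5.1.2 and not dosing breaches 4.5.4.

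**Can the maximum be reached while pH is still low?** Inputs from 4.5.1.2: 50 ml per infusion, 30 to 60 minutes to infuse, gas 1 to 2 hours afterwards, 500 ml maximum. Assumptions: repeat doses are also 50 ml, each starts as soon as the gas is read, and the 24 hours run from the first dose.

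- Doses to the maximum: 500 / 50 = 10.
- Shortest cycle: 0.5 + 1 = 1.5 h. The tenth dose starts at 9 × 1.5 = 13.5 h and ends at 14 h. The next gas is at 15 h, leaving 24 − 15 = 9 h in which no dose fits within the maximum.
- Longest cycle: 1 + 2 = 3 h. Doses start at 0, 3, ..., 21 h, which is 8 doses or 400 ml, so the maximum is not reached.

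Whether the conflict at the maximum arises therefore depends on pace, within the range the text allows. Section 4.5.3 confirms that it is expected in some participants: its second KRT criterion covers pH <7.25 after 24 hours of treatment at the 500 ml maximum. That section asks for at least two criteria as a guide and leaves the decision to the clinician, so such a participant may still be in the intervention period.

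**Can a reading below 7.30 go with a gas unlike the one at entry?** This uses the Henderson-Hasselbalch equation with usual constants, which are an assumption and not in the protocol: HCO3 = 0.0307 × PaCO2 (mmHg) × 10^(pH − 6.1), with 1 kPa = 7.5006 mmHg.

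- pH 7.28, 8 kPa: 0.0307 × 60.0 × 15.14 = 27.9 mmol/L.
- pH 7.28, 9 kPa: 0.0307 × 67.5 × 15.14 = 31.4 mmol/L.

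Both lie outside the entry limits in section 4.3.1 (PaCO2 <6.5 kPa, bicarbonate ≤20 mmol/L), yet both call for drug under 4.5.4.

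Bicarbonate above 20 mmol/L does not by itself identify a non-metabolic state. At pH 7.30 and 5.6 kPa, inside the entry PaCO2 limit, the equation gives 0.0307 × 42.0 × 15.85 = 20.4 mmol/L, and section 1.3 says the drug itself raises bicarbonate. The example shows only that pH alone discards information the schedule tells clinicians to use.

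**The case against.** The strongest defence is that 4.5.4 is shorthand. The dosing sections agree with each other: 4.5.1.3 and the Summary send the reader to the schedule, and the schedule names pCO2, HCO3 and clinical status. Section 4.6.1 lets a physician withdraw a participant from randomised treatment on clinical judgement. A query under 4.5.4 invites justification, and a dose held under the schedule has one. No sanction is attached. The flow diagram is not reproduced in the text available and may carry further conditions. Section 4.5.4 also does not say whether adherence is counted per reading or per participant.

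Much of this stands, and it rules out stronger readings. A reader might infer from 4.5.1.3 that any later pH <7.3, including a hypercapnic one, automatically requires study drug. It does not, because the cross-reference to the schedule brings in the other conditions. Nor is 90 days the usual length of exposure: it is the outer limit, and unit discharge or KRT ends the period sooner. A reader might also take section 1.2 as a warning about hypercapnic patients in particular, but CO2 accumulation is listed there as a general possible side effect.

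What the defence does not remove is the wording of 4.5.4. Withdrawal under 4.6.1 concerns the participant's treatment, not a single held dose. An episode that can be justified after a query has still been scored as non-adherent. If the diagram does contain a CO2 check, it would agree with 4.5.1.2 and leave 4.5.4 as the section out of step.

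**Conclusion.** The point holds as a contradiction between the adherence definition in 4.5.4 and the dosage schedule in 4.5.1.2. At the 24-hour maximum the two cannot both be satisfied. For pCO2 and clinical status, a decision the schedule allows is scored as a failure. The error runs one way: measured adherence in the intervention arm is understated, assuming readings below 7.30 are judged one by one, which the wording suggests but does not state.

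Its size is unknown, because the protocol does not say how often doses would be held. The consequence lies in monitoring: site reports, central monitoring, site-visit selection and the DMEC's view of adherence.

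Two further inferences are not supported. The mortality comparison is not biased by this: section 5.2.2 specifies intention to treat, the adherence definition does not alter the analysis set, and any harm from delivering the allocated strategy is part of the effect being estimated. Nor does the text show that the pilot stop/go decision is distorted. Section 3.3 uses the proportion receiving allocated treatment and does not say that it is computed from the 4.5.4 definition.

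**What to change.** - Reconcile the Summary, sections 4.5.1.2, 4.5.1.3 and 4.5.4, and the intervention flow diagram, so that one rule governs what follows a reading of pH <7.30. What that rule should be is for the clinical investigators; no threshold is proposed here.
- In 4.5.4, define intervention-arm adherence as delivery according to the dosage schedule. A dose withheld on grounds the schedule names, or because the stated maximum has been reached, is then not scored as non-adherent. State whether the count is per reading or per participant.
- When a dose is withheld at pH <7.30, record the reason, with PaCO2 and bicarbonate from the same gas. Section 4.9.3 already provides for adherence data without itemising them, so some of this may already be collected.
- If adherence has already been reported under the present wording, recompute it where the data allow, or label the two definitions separately.

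The cost is a wording amendment to a few sections and at most three data fields (reason, PaCO2, bicarbonate). No extra blood gas or procedure is needed, and the sample size and primary analysis do not change.
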